1.3 Schedule of Activities

Table 1. Schedule of Activities

Procedures	Pre-treatment		Treatment					Follow-up	
	Screening Days -36 to -1, Study Visit 1	Run-in Period ^a Days -15 to -1, Study Visit 2	Baseline Day 1, Study Visit 3	Day 8 (± 1 day) Study Visit 4	Day 15 (± 1 day) Study Visit 5	Day 22 (± 1 day) Study Visit 6	Day 29 (± 1 day) End of Treatment ^b /Early Termination ^b Study Visit 7	Day 43 (± 3 days) End of Study Study Visit 8	
Informed consent	X								
Demographics	X								
Medical and surgical history	X								
Rome IV assessment	X								
Concomitant medication review	X	X	X	X	X	X	X	X	
Adverse event review and evaluation		X	----- continuous -----					X	
Physical examination ^c	X		X				X		
Height, weight, and body mass index	X ^d		X		X		X	X	
Vital signs	X		X	X	X	X	X	X	
12-lead electrocardiogram	X						X		
Clinical safety laboratory tests ^e	X		X		X		X	X	
HIV, HCV/HBV testing	X								
Urine pregnancy test	X		X				X	X	
C-reactive protein and erythrocyte sedimentation rate tests	X		X		X		X	X	
Biomarker sample collection			X		X		X	X	
Pharmacokinetic sample collection ^f			X	X	X	X			
Worst abdominal pain	X	X ^g	X	----- ^h -----					X ^h
Bristol Stool Form Scale	X	X ^g	X	----- ^h -----					X ^h

Procedures	Pre-treatment		Treatment					Follow-up
	Screening Days -36 to -1, Study Visit 1	Run-in Period ^a Days -15 to -1, Study Visit 2	Baseline Day 1, Study Visit 3	Day 8 (± 1 day) Study Visit 4	Day 15 (± 1 day) Study Visit 5	Day 22 (± 1 day) Study Visit 6	Day 29 (± 1 day) End of Treatment ^b /Early Termination ^b Study Visit 7	
Spontaneous bowel movements (total number of stools)		X ^g	X ^h	----- ^h	----- ^h	----- ^h	----- ^h	X ^h
IBS-GS		X ^g	X ^h	----- ^h	----- ^h	----- ^h	----- ^h	X ^h
Rescue medications		X ^g	X ^h	----- ^h	----- ^h	----- ^h	----- ^h	X ^h
IBS-SS			X				X	X
Eligibility review	X		X					
Randomization			X					
Administration of investigational product			Day 1	-----	-----	-----	-----	Day 28

HBV = hepatitis B virus; HCV = hepatitis C virus; HIV = human immunodeficiency virus; IBS-GS = Irritable Bowel Syndrome Global Scale;
 IBS-SS = Irritable Bowel Syndrome Severity Score.

^a Run-in may be extended by up to one week in accordance with the investigators judgement. The full 5 week (Days -36 to -1) may be used to randomize eligible patients. However, efforts should be made to randomize eligible patients within 1 to 3 days after completing run-in period.

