^b Procedures performed at Visit 7/End of Treatment or upon Early Termination. Early Termination procedures are to be performed in close proximity to discontinuation of dosing for patients who are withdrawn from the study. Other procedures may be performed at Investigator or Sponsor discretion.
^c Full physical exam to be conducted at Screening. Symptom-directed physical examinations should be conducted at subsequent visits.
^d Height and body mass index to be collected at Screening Visit only.
^e Hematologic, complete serum chemistry, urinalysis panels and fecal calprotectin to be completed as noted in [Appendix 1](#). Patients should refrain from food or drinks (other than water) for at least 8 hours prior to obtaining a fasting glucose level.
^f Pharmacokinetic (PK) serial blood samples are to be collected on Day 1 and Day 15 at predose and at 0.5, 1, 2, and 4 hours postdose. If PK serial blood samples cannot be collected on Day 15, PK serial blood samples should be collected on Day 22. A predose sample will be obtained on all other Treatment Study Visits. Allowable sampling windows for PK blood draws will be 30 minutes prior to dosing for the predose sample, then ± 5 minutes for 0.5 and 1 hour postdose, and ± 10 minutes for 2 and 4 hours postdose.
^g Data will be collected daily for entire Run-in Period.
^h Data will be collected daily until Early Termination or until End-of-Study Visit, whichever is later.

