4.1.3 Replacement of Patients

Patients who sign the ICF and are randomized but do not receive the investigational product may be replaced. Once randomized, patients who have received at least 1 dose of investigational product and are withdrawn from therapy before completing 28 days of dosing or are discontinued from the study for any reason will not be replaced.

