2. STUDY OBJECTIVES AND ENDPOINTS

OBJECTIVES	ENDPOINTS
Primary	

 • To evaluate in patients with IBS-D the abdominal pain response to BOS-589 after 4 weeks of treatment, relative to Placebo. • To evaluate the overall safety and tolerability of BOS-589 in the treatment of IBS-D during 4 weeks of treatment, relative to Placebo. 	
 • 24-hour worst abdominal pain scores (WAP) at Day 29 compared to baseline (averaged over the week prior to each respective timepoint). • Incidence of adverse events (AEs) serious adverse events (SAEs), discontinuations because of AEs, and any treatment-related severe AEs.
Secondary	

 • To evaluate the treatment effect of BOS-589 on defecation after 4 weeks, relative to Placebo. • To evaluate the treatment effect of BOS-589 on IBS-related signs and symptoms. • To evaluate the steady-state PK of BOS-589. 	
 • Change in stool consistency, measured by the daily Bristol Stool Form Score (BSFS) at Day 29 compared to baseline (averaged over the week prior to each respective timepoint). • Change in stool frequency, measured by the total number of spontaneous bowel movements in 24 hours at Day 29 compared to baseline (averaged over the week prior to each respective timepoint). • Change in the IBS Severity Score (IBS-SS) at Day 29 compared to baseline. • Change in the IBS Global Scale (IBS-GS) at Day 29 compared to baseline (averaged over the week prior to each respective timepoint). • Maximum observed plasma concentration (C_{max}); time to C_{max} (T_{max}); minimum plasma concentration (C_{min}); area under the concentration versus time curve (AUC) from time zero to 4 hours postdose (AUC_{0-4}); AUC from time zero to the last quantifiable concentration (AUC_{0-t}).

Additional Objectives	Additional Endpoints
Exploratory (not included in protocol amendment 2 [version 3.0] dated 12 Aug 2019)	

 • To explore the treatment effect of BOS-589 in terms of weekly responders after 4 weeks of treatment, relative to Placebo. 	
 • Number of patients who are weekly responders, defined by both an abdominal pain intensity weekly responder (decrease in the weekly

Additional Objectives	Additional Endpoints

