5.7. Multiple Assessments and Visit Windows

If there are multiple assessments at a scheduled visit, then the last assessment will be used in the analysis.

Nominal visits (e.g., those identified by the study eCRF) will be the basis of summarization and statistical analysis; visit windows for each scheduled visit can be found in the Schedule of Activities from the protocol. Unscheduled data may be included in summaries of baseline and maximum/minimum change values; summaries of specific abnormalities any time post-baseline; and patient data listings.

Sponsor: Boston Pharmaceuticals, Inc.
Protocol Number: BOS-589-201
Version and Date: Version 1.2 12NOV2020

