7. EFFICACY

Efficacy analyses will be conducted using the ITT and PP Analysis Sets.

All available efficacy data will be provided in by-patient data listings on all ITT patients.

The efficacy objectives of the study are to evaluate the effect of BOS-589, relative to Placebo after 4 weeks of therapy, on pain, defecation, and key IBS-D related signs and symptoms.

During the 4 weeks of the double-blind treatment phase, patients will be required to access their electronic diary every day, preferably at the same time each day, to record IBS-D symptom data and information related to their bowel function and rescue medication use.

For all efficacy endpoints, the Day 29 visit change from baseline is the main timepoint of interest. However, unless stated otherwise, data will be presented for each planned visit (Baseline/Day 1, Day 8, Day 15, Day 22, Day 29, and Day 43).

For efficacy endpoints collected daily, the baseline score will be the average of non-missing scores reported for the last 7 days prior to the date where eligibility and run-in criteria pertaining to IBS-D symptom and bowel function have been met. The Day 29 visit score will be the average of non-missing scores reported during the 7 days prior to the Day 29 visit. The Day 8 visit, Day 15 visit, Day 22 visit, and Day 43 visit scores are calculated in a similar manner. If there are missing daily scores on any day, the visit score will be averaged from all the non-missing values during the 7 days prior to the visit. No imputation of the missing values will be made. For the Day 29 calculation only, a window of ± 14 days relative to actual calculated day 29 from dosing will be applied such that any Day 29 visit occurring outside that window will be excluded.

Sponsor: Boston Pharmaceuticals, Inc.
Protocol Number: BOS-589-201
Version and Date: Version 1.2 12NOV2020

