9. SAFETY

Unless otherwise specified, all safety analysis reporting will be based on the SAF Analysis Dataset. For safety analyses, Day 29 represents measures taken at end of treatment/early termination while Day 43 represents measures taken at the end of study.

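### The SAP accepts a Day 29 visit anywhere from Day 15 to Day 43 and scores the 7 days before it, so the primary 4-week pain score can contain no day from week 4

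*SAP*

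**What the plan says.** SAP section 2 defines the primary efficacy endpoint as "24-hour worst abdominal pain scores (WAP) at Day 29 compared to baseline (averaged over the week prior to each respective timepoint", and the matching objective is pain response after 4 weeks of treatment. The protocol states the same endpoint and objective.

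SAP section 7 gives the scoring rule: "The Day 29 visit score will be the average of non-missing scores reported during the 7 days prior to the Day 29 visit". For Day 29 only, it adds a margin of two weeks either way (± 14 days), in these words: "days relative to actual calculated day 29 from dosing will be applied such that any Day 29 visit occurring outside that window will be excluded". Section 7.1.1 carries this visit-based score into the hierarchical t-tests.

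The protocol's Schedule of Activities places the visit at "Day 29 (± 1 day) End of Treatment", in a column shared with Early Termination. SAP section 5.7 analyses nominal visits and says that "visit windows for each scheduled visit can be found in the Schedule of Activities from the protocol". Planned dosing runs from Day 1 to Day 28; Protocol 4.1.3 likewise speaks of patients "withdrawn from therapy before completing 28 days of dosing". The diary continues beyond that: "Data will be collected daily until Early Termination or until End-of-Study Visit, whichever is later".

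**The concern.** A visit date is an administrative event. The endpoint is a week of diary data at a fixed time from first dose. By anchoring the score to the visit and tolerating two weeks either way, the SAP lets the diary week drift away from week 4. A late visit brings in post-dose days; an early one brings in week 2 or week 3. Post-dose days pull the estimate toward no difference to the extent that the effect fades after the last dose, and a mixture of weeks no longer measures response after 4 weeks.

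The early side turns on something the SAP does not settle. Section 9 says "For safety analyses, Day 29 represents measures taken at end of treatment/early termination", but there is no such statement for efficacy. If an Early Termination visit is taken as the efficacy Day 29 visit, a week-2 or week-3 average enters the primary endpoint. That would be a carry-forward in all but name, although section 7 says missing values are not imputed.

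SAP section 3.2 lists changes from the protocol and does not mention this rule. The front matter of v1.2 is not available to us, so a rationale may be recorded there.

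**Working it through.** **Inputs.** Study Day 1 is the first dose (SAP 5.2). Scored days for a visit on day V are V−7 to V−1 (SAP 7). Accepted visits are Day 29 ± 14 (SAP 7). The target week is Days 22-28, the 7 days before Day 29. The last planned dose is on Day 28 (Protocol 1.3). For power: SD 3, difference 1.6, two-sided alpha 0.05, N = 120 for the calculation and 132 randomized (SAP 3.4).

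**Accepted range.** 29 − 14 = 15 and 29 + 14 = 43, so there are 43 − 15 + 1 = 29 possible visit days.

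**Overlap with Days 22-28.** For each V, count the days from V−7 to V−1 that fall in Days 22-28, and those that fall after Day 28.

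| Visit day | Days scored | Days from 22-28 | Days after 28 |
|---|---|---|---|
| 15 | 8-14 | 0 | 0 |
| 22 | 15-21 | 0 | 0 |
| 23 | 16-22 | 1 | 0 |
| 26 | 19-25 | 4 | 0 |
| 28 | 21-27 | 6 | 0 |
| 29 | 22-28 | 7 | 0 |
| 30 | 23-29 | 6 | 1 |
| 32 | 25-31 | 4 | 3 |
| 35 | 28-34 | 1 | 6 |
| 36 | 29-35 | 0 | 7 |
| 43 | 36-42 | 0 | 7 |

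- No overlap: visits on Days 15-22 (8 days) and 36-43 (8 days), 16 of 29 in all.
- At least 4 of 7 days: visits on Days 26-32, 7 of 29.
- All 7 days: a visit on Day 29 only.
- Within the protocol's ± 1 day (Days 28, 29, 30): 6, 7 and 6 of 7.
- Entirely after Day 28: visits on Days 36-43. Partly after Day 28 (1 to 6 days): visits on Days 30-35.

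At the two limits, the Day 29 score uses the same diary days as an on-schedule Day 15 score (Days 8-14) or Day 43 score (Days 36-42). Including the visit day itself (V−6 to V) still gives 16 zero-overlap visit days, namely 15-21 and 35-43. Entries recall the past 24 hours, which can shift the on-drug counts by at most one day.

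**Power, for scale only.** Hypothesis 1 compares 80 active with 40 placebo at N = 120. The standard error is 3 × √(1/80 + 1/40) = 0.581, so the noncentrality is 1.6 / 0.581 = 2.75 on 118 degrees of freedom. Noncentral-t power is 78.0%, consistent with the SAP's approximate 80%. If a share f of patients loses a fraction g of the effect, the mean difference becomes 1.6 × (1 − f × g).

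| f | g | Difference | Power, 80 vs 40 | Power, 88 vs 44 |
|---|---|---|---|---|
| 0 | – | 1.60 | 78% | 82% |
| 5% | 1 | 1.52 | 74% | 78% |
| 10% | 0.5 | 1.52 | 74% | 78% |
| 10% | 1 | 1.44 | 69% | 73% |

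The values of f and g are assumptions; the documents give neither.

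**The case against.** The strongest reply is that ± 14 days is an outer limit, not the schedule. Visits are planned for Day 29 ± 1 day, where 6 or 7 of the 7 target days are captured. Because section 5.7 works with nominal visits and states no cutoff for a late one, the rule arguably narrows what would otherwise be accepted. On this view 16 of 29 counts calendar days, not patients, and the real effect may be very small. That stands as a caution about size. It does not defend the rule: the diary is daily, so a straggler's week-4 entries exist whatever the visit date, and no wide window is needed to recover them.

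Several narrower points also stand.

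- The off-drug counts assume dosing stops on Day 28. The SAP computes exposure from actual dates and does not say what happens to dosing if the visit is late.
- SAP section 4 includes all data regardless of treatment duration, so off-drug data are not a fault in themselves. The fault is timing.
- Weeks 2 and 3 are planned on-drug weeks, so the no-effect assumption does not naturally fit early visits.
- The Early Termination route is a possibility the SAP leaves open, not a stated rule.
- Late visits bias toward no difference; no inflation of false positives is shown.

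The per-protocol analysis could remove badly mistimed visits, but only at discretion, and it does not repair the ITT test.

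**Conclusion.** The concern holds. On the current SAP text, a primary score labelled Day 29 may come from any 7-day span between Days 8-14 and Days 36-42. More than half of the accepted visit days (16 of 29) yield a score with no week-4 data. This is inconsistent with the 4-week objective and with the protocol's ± 1 day schedule. The finding concerns what the rule permits; how often it happens is not stated, and the power figures only show scale under assumed shares. The late-visit part needs no assumption about Early Termination, because diary entry continues through follow-up. Since the rule defines the primary variable and is cheap to correct, it must be fixed even if few patients turn out to be affected.

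**What to change.** For the daily-diary endpoints, define the Day 29 score as the mean of non-missing entries dated study Days 22-28 from first dose, whatever the date of Visit 7 or Early Termination. Score the other visits the same way: Days 1-7 for Day 8, 8-14 for Day 15, 15-21 for Day 22 and 36-42 for Day 43. Delete the ± 14-day rule for these endpoints. IBS-SS is completed at the visit and should keep a visit window. Record the definition in SAP section 3.2.

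Patients with no entry on Days 22-28 are missing under the existing no-imputation rule; report their number by cohort. Patients who stop drug early but keep the diary are still scored on Days 22-28, in line with section 4.

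The cost is SAP wording and one derivation change, with no new data. SAP v1.1 already used Days 22-28, and section 5.2 already makes treatment start the efficacy reference date, so the rule can be programmed. The downside is that a few patients with an early visit and no later entries move from scored to missing, which may slightly reduce n in the t-test.

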7.1. Primary Efficacy Endpoint and Analyses

7.1.1. Worst Abdominal Pain

The primary efficacy endpoint will be defined as a change in the 24-hour WAP score at the Day 29 visit compared to baseline (averaged over the week prior to the visit). The 24-hour WAP score will be a patient-reported score of their WAP in the past 24 hours on a 0 to 10 scale, where 0 corresponds to no pain and 10 corresponds to worst imaginable pain. Patients will be asked to rate their WAP in the past 24 hours every day for the entire Run-in period and the 4-week double-blind treatment period.

This is a proof-of-principle study in which a hierarchical hypothesis test will be employed for the primary efficacy endpoint. The mean change in 24-hour WAP at the Day 29 visit from baseline (averaged over the week prior to the visit) will be measured as a continuous variable and compared between cohorts in the following testing order using a t-test of equal variances and a two-tailed alpha of 0.05:

Hypothesis 1:

Active Treatment (Cohort 1 + Cohort 2) versus Placebo (Cohort 3);

$$H_0: \mu_1 = \mu_2$$

$$H_1: \mu_1 \neq \mu_2$$

The null hypothesis will be that there is no difference in the mean change in 24-hour WAP score at the Day 29 visit from Baseline (averaged over the week prior to the visit) between active treatment and Placebo. The alternative hypothesis will be that there is a difference in the mean change in 24-hour WAP score at the Day 29 visit from Baseline (averaged over the week prior to the visit) between active treatment and Placebo. The test statistic is:

$$t = \frac{\bar{x}_1 - \bar{x}_2}{\sqrt{s^2(\frac{1}{n_1} + \frac{1}{n_2})}}$$

\bar{x}_1 and \bar{x}_2 are the sample means of change at the Day 29 visit from Baseline in 24-hour WAP score (averaged over the week prior to the visit), s^2 is the pooled sample variance assuming equal variance, n_1 and n_2 are the sample sizes, and the degree of freedom is $n_1 + n_2 - 2$.

If statistically significant at $P < 0.05$, then proceed to Hypothesis 2.

Hypothesis 2:

Cohort 1 (High Dose) versus Cohort 3 (Placebo);

Sponsor: Boston Pharmaceuticals, Inc.
Protocol Number: BOS-589-201
Version and Date: Version 1.2 12NOV2020

If statistically significant at $P < 0.05$, then proceed to Hypothesis 3.

Hypothesis 3:

Cohort 2 (Low Dose) versus Cohort 3 (Placebo);

If statistically significant at $P < 0.05$ then, proceed to Hypothesis 4.

Hypothesis 4:

Cohort 1 (High Dose) versus Cohort 2 (Low Dose).

Methodology for hypotheses 2 to 4 will be similar to that described for hypothesis 1.

The patient-reported 24-hour WAP scores and change from baseline scores (averaged over the week prior to each visit) will be summarized descriptively by cohort for each scheduled visit. Box plots of the 24-hour WAP scores (averaged over the week prior to each visit) will also be presented by cohort at each scheduled visit. Line plots of 24-hour WAP change from baseline scores (averaged over the week prior to each visit) will also be presented by cohort at each scheduled visit.

To evaluate the treatment effects in the subset of patients with fecal calprotectin under 50mcg/g at screening, this analysis of worst abdominal pain will be repeated as a sensitivity analysis on this subgroup.

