9.4.1 Efficacy Analyses

9.4.1.1 Primary Endpoint

This is a proof-of-principle study in which a hierarchical hypothesis test will be employed for the primary efficacy endpoint, defined as a change in the 24-hour WAP score at Day 29 compared to baseline (averaged over the week prior to each respective timepoint). Mean change from baseline will be measured as a continuous variable and compared between treatment groups in the following testing order using a t-test of equal variances and a two-tailed alpha of 0.05:

Hypothesis 1:

Active Treatment Group (Cohort 1 + Cohort 2) versus PBO (Cohort 3);

If statistically significant at $P < 0.05$, then proceed to Hypothesis 2.

Hypothesis 2:

Cohort 1 (High Dose) versus Cohort 3 (PBO);

If statistically significant at $P < 0.05$, then proceed to Hypothesis 3.

Hypothesis 3:

Cohort 2 (Low Dose) versus Cohort 3 (PBO);

If statistically significant at $P < 0.05$ then, proceed to Hypothesis 4.

Hypothesis 4:

Cohort 1 (High Dose) versus Cohort 2 (Low Dose).

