3.4. Sample Size Considerations

This is a phase 2a study in which a hierarchical hypothesis test will be employed for the primary efficacy endpoint. The primary endpoint is defined as a change in the 24-hour WAP score at Day 29 compared to baseline (averaged over the week prior to each respective timepoint). Mean change from baseline will be measured as a continuous variable and compared between cohorts in a hierarchical testing order using a t-test of equal variances and a two-tailed alpha of 0.05.

Sponsor: Boston Pharmaceuticals, Inc.
Protocol Number: BOS-589-201
Version and Date: Version 1.2 12NOV2020

The sample size was based on the first hypothesis test in the hierarchical plan, with approximately 80% power, two-sided alpha of 0.05, and a standard deviation (SD) of 3 points on the numeric rating scale to detect a 1.6 minimum change between cohorts (N = 120 patients). To account for attrition and a potential higher Placebo rate, a total of 132 patients will be randomized to one of 3 cohorts in a 1:1:1 ratio (44 patients per cohort).

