7.2. Secondary Efficacy Endpoints and Analyses

7.2.1. Stool Consistency

Patients will be asked to record daily stool consistency according to the BSFS most representative stool consistency in the past 24 hours and the worst stool consistency (defined as the loosest stool with the highest BSFS score) in the past 24 hours. The patient-reported BSFS consistency score, based on a 1 to 7 scale where 1 corresponds to a hard stool and 7 corresponds to watery diarrhea (10), can be found in [Appendix 2](#).

The patient-reported stool consistency scores and change from baseline scores (averaged over the week prior to each visit) will be summarized descriptively by cohort for each scheduled timepoint. Pooled active treatment data will be compared to Placebo for the analyses, and by cohort, using a t-test of equal variances and a two-tailed alpha of 0.05 specified in section 7.1.1 for reference. Box plots of the BSFS scores (averaged over the week prior to each visit) will also be presented by cohort for each scheduled visit. Line plots of the BSFS change from baseline values (averaged over the week prior to each visit) will also be presented by cohort for each scheduled visit. Analyses for the most representative stool consistency in the past 24 hours and worst (loosest) stool consistency in the past 24 hours will both be presented.

Sponsor: Boston Pharmaceuticals, Inc.
Protocol Number: BOS-589-201
Version and Date: Version 1.2 12NOV2020

To evaluate the treatment effects in the subset of patients with fecal calprotectin under 50mcg/g at screening, this analysis of BSFS most representative consistency and BSFS worst consistency will be repeated as sensitivity analyses on this subgroup as described in section 7.1.1.

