7.2.2. Stool Frequency

Patients will be asked to record stool frequency based on the total number of spontaneous bowel movements in the past 24 hours. Bowel movement frequency and change from baseline (averaged over the week prior to each visit) will be analyzed and summarized using the same method as the secondary endpoint described in Section 7.2.1.

To evaluate the treatment effects in the subset of patients with fecal calprotectin under 50mcg/g at screening, this analysis of stool frequency will be repeated as a sensitivity analysis on this subgroup as described in section 7.1.1.

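### Hypothesis 1 is a 2:1 comparison (88 v 44) tested with a pooled variance, so its interval coverage and power, and its error rate for equal means, rest on an unchecked assumption of equal SDs.

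*SAP*

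**What the plan says.** Protocol 9.4.1.1 compares mean change in worst abdominal pain "using a t-test of equal variances and a two-tailed alpha of 0.05". SAP 3.4, 4.3 and 7.1.1 name the same test. SAP 7.1.1 writes out the statistic: the variance term "is the pooled sample variance assuming equal variance", with n1 + n2 - 2 degrees of freedom. The null hypothesis is equality of the two mean changes; nothing is said about spread.

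Hypothesis 1 combines the 200 mg and 50 mg cohorts and compares them with placebo. It must be significant before Hypotheses 2 to 4 are tested. With 1:1:1 allocation and 44 per cohort it is 88 v 44 as randomised, or 80 v 40 at the N = 120 behind the power statement. SAP 3.4 sizes the trial on this comparison with "approximately 80% power, two-sided alpha of 0.05, and a standard deviation (SD) of 3 points on the numeric rating scale". No SD is given for active and placebo separately.

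SAP 4 plans 95% confidence intervals as a general rule. SAP 7.2.1 applies the same test to stool consistency, "using a t-test of equal variances and a two-tailed alpha of 0.05 specified in section 7.1.1 for reference", and SAP 7.2.2 to 7.2.4 carry it to the other secondary endpoints. SAP 4.3 calls the secondary p-values descriptive. Neither document has a variance check or a separate-variance analysis. The only sensitivity analysis named for the primary endpoint repeats the same test in the low fecal calprotectin subgroup.

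**The concern.** With equal group sizes a pooled-variance t-test tolerates unequal variances well. At 2:1 it does not, because the larger group dominates the pooled estimate while the smaller group contributes most of the true variance of the difference. If placebo varies more than active, the standard error is too small: intervals are too narrow and the null of equal means is rejected too often. If active varies more, the standard error is too large and power is lost.

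The SDs could separate if the drug works. Patients moving toward the zero end of the scale would compress the active SD. Benefit confined to some patients, or two doses with different effects, would widen it. At stake are the interval and power for the comparison that gates all the others.

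**Working it through.** **Inputs.** From SAP 3.4 and 7.1.1: n = 88 v 44 (80 v 40 at N = 120), SD 3, difference 1.6, two-sided alpha 0.05, pooled variance. Assumed, because the documents do not give them: separate active and placebo SDs, with the larger set at 3 and the other between 2 and 3.

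**1. The plan's own power.** SE = 3 × √(1/80 + 1/40) = 0.581, and 1.6/0.581 − 1.96 = 0.79, so power is 78.6% (noncentral t: 78.0%). At 88 v 44, SE = 0.554 and power is 82.3% (noncentral t: 81.8%). The stated figure of about 80% is reproduced.

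**2. Effect of unequal SDs.** The pooled test estimates the variance of the difference as

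V_pooled = s_p² × (1/n1 + 1/n2), where on average s_p² = [(n1 − 1)σ1² + (n2 − 1)σ2²]/(n1 + n2 − 2).

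The true variance is V_true = σ1²/n1 + σ2²/n2. With r = √(V_pooled/V_true), the actual two-sided error is approximately 2 × [1 − Φ(1.96 r)].

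Example, active SD 2.7 and placebo SD 3 at 88 v 44:
- s_p² = (87 × 7.29 + 43 × 9)/130 = 7.856
- V_pooled = 7.856 × (1/88 + 1/44) = 0.2678
- V_true = 7.29/88 + 9/44 = 0.2874
- r = 0.965, error 5.8%

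Simulation from normal data (1,000,000 trials per setting) agrees. At 88 v 44:

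| SD active / placebo | Pooled: error | Pooled: 95% CI coverage | Welch: error |
|---|---|---|---|
| 3 / 3 | 5.0% | 95.0% | 5.0% |
| 2.7 / 3 | 5.8% | 94.2% | 5.0% |
| 3 / 2.7 | 4.2% | 95.8% | 5.0% |
| 2.5 / 3 | 6.5% | 93.5% | 5.0% |
| 3 / 2.5 | 3.8% | 96.3% | 5.0% |
| 2 / 3 | 8.5% | 91.5% | 5.0% |
| 3 / 2 | 2.6% | 97.4% | 5.0% |

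At 80 v 40 the results agree to within about 0.1 point. At 44 v 44, r is 1 for any pair of SDs, and the simulated pooled error stays at 5.0% to 5.1% over these settings.

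**3. Plausible SD ratios.**
- *Doses that differ.* If one dose has a 1.6-point effect and the other none, pooling adds (1.6/2)² = 0.64 to the active variance. √9.64 = 3.10 against 3, and the rejection rate is 4.7%.
- *Floor of the scale.* Illustrative assumptions: baseline about N(5.5, 1.3) truncated to the 3 to 8 entry range, latent change SD 2 to 3, latent placebo change −1 to −2, a further 1.6-point shift on drug, scores clipped to 0 to 10. The active/placebo SD ratio of the change is then about 0.89 to 0.95. At 0.9, coverage is 94.2%.

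**4. Power for a 1.6-point difference, 88 v 44.**

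| SD active / placebo | Pooled | Welch |
|---|---|---|
| 3 / 3 | 81.8% | 81.5% |
| 3 / 2.5 | 87.0% | 89.3% |
| 3 / 2 | 91.6% | 95.1% |
| 2.7 / 3 | 85.9% | 83.9% |
| 2.5 / 3 | 88.1% | 85.3% |

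In the last two rows the pooled advantage comes from a test running above 5%. At 80 v 40 with equal SDs the figures are 78.0% and 77.6%.

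**The case against.** The strongest reply is that the inflated error rates need a null that the suggested mechanisms do not produce. If the drug is inert, randomised arms share one distribution and the pooled test holds 5%. A floor effect, benefit in a subset, or differing doses would move the means as well as the spread, unless gains and harms happened to cancel. A reader might infer from the 8.5% figure that an ineffective drug has that chance of opening the hierarchy. The documents do not support this: the figure describes a drug with exactly zero mean effect that cuts the SD by a third. This objection stands, and it moves the weight to coverage and power when the drug works.

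A reader might also infer that the SDs are known or likely to differ, or that the whole hierarchy and the secondary endpoints are compromised. The single SD of 3 is no evidence either way. Hypotheses 2 to 4 compare equal arms as planned, and the secondary tests are for reference only. The SAP also reports SDs by cohort and for combined active, with box plots by cohort, so a marked imbalance would be visible. That helps a reader but does not correct the test or the interval.

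What the objection leaves untouched is that equality is assumed in an unbalanced primary comparison, without justification or check.

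**Conclusion.** The point holds as a modest robustness weakness confined to Hypothesis 1. Its interval coverage and power, and its error rate for a null of equal means, depend on equal active and placebo SDs. At ratios near 0.9 or 1.1 the shift is under 1 point (4.2% to 5.8% error, 95.8% to 94.2% coverage). The 8.5% and 2.6% results, at 2 v 3 and 3 v 2, mark the extremes and are not expectations. All of this rests on assumed SDs and normal data. The 88 v 44 split is as randomised; missing scores are not imputed, so analysed numbers may be lower, but the effect depends mainly on the group-size ratio. Unequal dropout could make Hypotheses 2 to 4 somewhat unbalanced. The plan's power figure is sound under its own equal-SD assumption.

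**What to change.** Before unblinding, name the unequal-variance (Welch-Satterthwaite) t-test and its confidence interval for Hypothesis 1 in SAP 3.4, 4.3 and 7.1.1 and in protocol 9.2 and 9.4.1.1. Keep the pooled-variance result as supportive. No change is needed for the descriptive secondary tests.

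Protocol 9.4 gives the SAP precedence on analysis details but sends major modifications of the primary analysis to a protocol amendment. The sponsor should decide whether this change qualifies. If it prefers not to amend, it should pre-specify Welch as the sensitivity analysis for Hypothesis 1.

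If the SDs are equal, the cost is 0.3 points of power at 88 v 44 and 0.4 at 80 v 40. If the active SD is 2.5 to 2.7 against 3, Welch rejects about 2 to 3 points less often than the pooled test, whose rate is inflated there. If the active SD is the larger, Welch gains power: 2.3 points at 3 v 2.5 (87.0% to 89.3%, 88 v 44).
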